### **11.3 Exploratory Objectives**

Descriptive methods will be used to analyze the exploratory objectives. Circulating tumor DNA alterations and response category will be cross-tabulated. The mean and standard deviation of enumerated tumor cell characteristics will be reported separately for each response category. The mean and standard deviation at the time of radiographic progression will be reported for subjects with documented radiographic progression.

## 12 REGISTRATION GUIDELINES

**Patients must meet all of the eligibility requirements listed in Section 5 prior to registration.**

**Study related screening procedures can only begin once the patient has signed a consent form. Patients must not begin protocol treatment prior to registration.**

Treatment should start within five working days after registration.

To register eligible patients on study, complete a Clinical Trials Office Patient Registration Form and submit to [[contact]](mailto:[contact]).

## 13 DATA SUBMISSION SCHEDULE

The Case Report Forms (CRFs) are a set of (electronic or paper) forms for each patient that provides a record of the data generated according to the protocol. CRF's should be created prior to the study being initiated and updated (if applicable) when amendments to the protocol are IRB approved. These forms will be completed on an on-going basis during the study. The medical records will be source of verification of the data. During the study, the CRFs will be monitored for completeness, accuracy, legibility and attention to detail by a member of the Research Compliance Office. The CRFs will be completed by the Investigator or a member of the study team as listed on the Delegation of Duties Log. The data will be reviewed no less than annually by the Data and Safety Monitoring Committee. The Investigator will allow the Data and Safety Monitoring Committee or Research Compliance Office personnel access to the patient source documents, clinical supplies dispensing and storage area, and study documentation for the above-mentioned purpose. The Investigator further agrees to assist the site visitors in their activities.

## 14 SPECIAL INSTRUCTIONS

### 14.1 Correlative Studies

To support exploratory objectives and correlative studies, blood and tissue samples will be collected at the time points indicated on the Schedule of Events. After completion of the described correlative studies, any remaining blood or tissue will be stored for future unspecified cancer research. With the participant's approval and as approved by the Institutional Review Board (IRB), de-identified biological samples will be stored at Huntsman Cancer Institute's Biorepository.

At the time of consent, subjects will be given the opportunity to authorize the biobanking of their remaining samples for use in future undisclosed research. During the conduct of the study, an individual participant can choose to withdraw consent to have biological specimens stored for future research. However, the withdrawal of consent with regard to biosample storage may not be possible after the study is completed.

Correlative studies will evaluate exploratory biomarkers predictive of response and resistance to treatment with rucaparib. Patients will have a baseline assessment at the time of enrollment.

#### **14.1.1 Collection of Blood for Correlative Analysis**

30-40 mL of blood will be collected at screening, C3D1, C7D1, and confirmed PSA Progression or EOT (whichever occurs first).

Testing may include, but is not limited to:

- Circulating tumor cells (CTC) detection, enumeration, and characterization
- Cytokine/chemokine/interferon assays
- Genomic analysis
- Proteomic analyses
- Flow Cytometry

Specimen collection and processing instructions can be found in the lab manual.

#### **14.1.2 Collection of Urine samples for Correlative Analysis**

For patients with an intact prostate, 10-20 mLs of urine will be collected at screening, C3D1, C7D1, and confirmed PSA progression or EOT (whichever occurs first). Prior to collection of the urine specimen a prostate exam will be performed by the treating physician.

Testing may include, but is not limited to:

- Androgen receptor isoform splice variant (AR-V7).

Specimen collection and processing instructions can be found in the lab manual.

#### **14.1.3 Collection of Tumor Tissue**

Available archival tissue will be used for correlative testing. If archival tissue is not available, a new biopsy will NOT be required. Archival tissue slides should not be cut until requested by the central lab.

An optional fresh biopsy will be obtained at the PSA Progression Confirmation Visit only for subjects who demonstrate radiographic progression. Up to 6 cores will be obtained.

Testing may include, but is not limited to:

- Multiomics platforms
- Immunohistochemistry
- Flow cytometry

Instructions for processing and analysis will be detailed in the lab manual.

#### **14.1.4 BRCAness Testing**

Genomic or genetic testing for 'BRCAness' will be confirmed with either blood or tissue based testing.

## 15 ETHICAL AND REGULATORY CONSIDERATIONS

### 15.1 Informed consent

Informed consent will be obtained from all research participants prior to performing any study procedures using the most recent IRB approved version.

### 15.2 Human Subjects Protections

#### 15.2.1 Participation of Children

Patients must be at least 18 years of age to participate.

#### 15.2.2 Participation of Subjects Unable To Give Consent

Patients must be able to provide informed consent and willing to sign an approved consent form that conforms to federal and institutional guidelines.

### 15.3 Institutional Review

Before study initiation, the investigator must have written and dated approval/favorable opinion from the IRB/IEC for the protocol, consent form, subject recruitment materials (eg, advertisements), and any other applicable patient-facing documents. The investigator should also provide the IRB/IEC with a copy of the Investigator Brochure or product labeling information.

The investigator or designee should provide the IRB/IEC with reports, updates and other information (e.g., expedited safety reports, amendments, and administrative letters) according to regulatory requirements or institution procedures. Data and Safety Monitoring Plan

A Data and Safety Monitoring Committee (DSMC) is established at Huntsman Cancer Institute (HCI) to ensure the well-being of patients enrolled on Investigator Initiated Trials that do not have an outside monitoring review. The roles and responsibilities of the DSMC are set forth in the NCI-approved Data and Safety Monitoring (DSM) plan. The activities of the committee include reviewing adverse events (including SAEs), deviations, important medical events, significant revisions or amendments to the protocol, and approving cohort/dose escalations. If the DSMC and/or the PI have concerns about unexpected safety issues, the study will be stopped and will not be resumed until the issues are resolved. The DSMC also reviews and approves audit reports generated by the Research Compliance Office.

This is a Phase II study classified as moderate risk per the NCI-approved DSM plan. Each moderate risk study may be assigned a physician member of the DSMC as medical monitor, or in rare cases, an external medical monitor. The medical monitor will be notified of all serious adverse events (SAEs). SAEs occurring in patients treated at HCI or its affiliates will also be reviewed by the full DSMC monthly. The full committee will also review all toxicities for patients on treatment and within 30 days of their last treatment on a quarterly basis.

Each moderate-risk study will be assigned a dedicated research compliance officer who will monitor the trial. Moderate-risk trials will be monitored by RCO personnel after the first patient is enrolled and every six months thereafter during active enrollment. The RCO

monitor will review the study status and summarize enrollment, toxicities, SAEs, dose escalation, statistical endpoints (e.g., stopping rules), deviations, etc. for the full DSMC membership at the regularly scheduled meetings. Amendments that increase risk, change dosing, or impact study objectives will be reviewed by the DSMC and approved by the PRMC and IRB. Moderate-risk trials will be formally reviewed by the DSMC after the first patient is enrolled and then semi-annually thereafter.

An initial audit of moderate-risk studies will be conducted by the RCO approximately one year after enrollment begins and annually thereafter. Audits of moderate-risk studies may be conducted more frequently as requested by the DSMC, IRB, PRMC, RCO management, or the PI.

## **15.4 Adverse Events / Serious Adverse Events**

This study will utilize the CTCAE (NCI Common Terminology Criteria for Adverse Events) Version 5.0 for AE and SAE reporting.

### **15.4.1 Adverse Events (AE)**

An adverse event is the appearance or worsening of any undesirable sign, symptom, or medical condition occurring after starting the study drug even if the event is not considered to be related to study drug. For the purposes of this study, the terms toxicity and adverse event are used interchangeably. Medical conditions/diseases present before starting study drug are only considered adverse events if they worsen after starting study drug. Abnormal laboratory values or test results constitute adverse events only if they induce clinical signs or symptoms, are considered clinically significant, or require therapy.

Collection of adverse events will begin after the first dose of study treatment and end 30 days after the last dose of study treatment.

Information about all adverse events, whether volunteered by the subject, discovered by investigator questioning, or detected through physical examination, laboratory test or other means, will be collected and recorded and followed as appropriate.

The occurrence of adverse events should be sought by non-directive questioning of the patient at each visit or phone contact during the study. Adverse events also may be detected when they are volunteered by the patient during or between visits or through physical examination, laboratory test, or other assessments. As far as possible, each adverse event should be evaluated to determine:

1. The severity grade based on CTCAE v.5.0 (grade 1-5)
2. Its relationship to the study drug(s) (definite, probably, possible, unlikely, not related)
3. Its duration (start and end dates or if continuing at final exam)
4. Action taken (no action taken; study drug dosage adjusted/temporarily interrupted; study drug permanently discontinued due to this adverse event; concomitant medication taken; non-drug therapy given; hospitalization/prolonged hospitalization)
5. Whether it constitutes an SAE

All adverse events will be treated appropriately. Such treatment may include changes in study drug treatment as listed in the dose modification section of this protocol (see Section

7.1 for guidance). Once an adverse event is detected, it should be followed until a new baseline is reached, death, or when patient is lost to follow up. Assessment should be made at each visit (or more frequently, if necessary) of any changes in severity, the suspected relationship to the study drug, the interventions required to treat it, and the outcome.

Information about common side effects already known about the rucaparib is described in the Drug Information section (Section 3) as well as Section 6.6 and Table 19 of Investigator Brochure. This information will be included in the patient informed consent and will be discussed with the patient during the study as needed.

All adverse events will be immediately recorded in the patient research chart.

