### 3.1.6 Adverse Events of Special Interest

A review of all reports of MDS and AML that have occurred in the entire clinical development program up to 10 April 2017 revealed a total of 10 reports in patients exposed to rucaparib in Studies CO-338-010, CO-338-017, and CO-338-014.

The rate of MDS/AML was 0.5% for patients on treatment and during the 28 day safety follow-up, and 0.9% for all patients including during the long-term safety follow-up (rate is calculated based on overall safety population of 1077 patients exposed to at least one dose of oral rucaparib in all clinical studies).

There was one case of AML in 189 patients exposed to placebo in Study CO-338-014.

All of the patients diagnosed with MDS or AML had received multiple cycles and regimens of prior chemotherapy, including platinum- and/or taxane-containing regimens. One patient had also received prior treatment with an alkylating agent (cyclophosphamide) and 2 patients had received radiation for breast cancer (1 patient received rucaparib and 1 received placebo). One patient was discontinued from rucaparib 14 months prior to MDS diagnosis and was treated with olaparib for 13 months between rucaparib discontinuation and MDS diagnosis. One patient discontinued rucaparib 9 months prior to MDS diagnosis and was treated with cisplatin and trabectedin for an unspecified time between rucaparib discontinuation and MDS diagnosis. Exposure to DNA-damaging therapies for ovarian and breast cancer present an increased risk of developing MDS or AML

In patients diagnosed with MDS, duration from start of primary disease treatment to diagnosis was between approximately 1 and 23 months (i.e., 35 days to approximately 693 days). In patients diagnosed with AML, duration from start of primary disease treatment to AML diagnosis was between approximately 3.5 and 28.5 months (i.e., 106 to 868 days). In the patient with MDS that evolved into AML, the duration of time from starting treatment with rucaparib to diagnosis of MDS was approximately 12.5 months (i.e., 380 days) and from start of rucaparib to diagnosis of AML was approximately 18 months (i.e., 541 days).

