### **7.1.1 Management of anemia including evaluation for MDS/AML and follow-up of patients who discontinue treatment with ongoing anemia**

- If the patient develops anemia CTCAE Grade  $\geq 3$ , rucaparib treatment should be held until the anemia improves to CTCAE Grade  $\leq 2$  whereupon daily dosing may then be resumed at either the same dose or a lower dose, per investigator discretion.
- If the duration of dosing is interrupted for  $> 14$  consecutive days due to anemia CTCAE Grade  $\geq 3$ , treatment should be permanently discontinued, unless otherwise agreed between the investigator and Clovis.
- In addition, if anemia CTCAE Grade  $\geq 3$  persists for  $> 14$  consecutive days, or a dependence upon blood transfusion occurs, then weekly complete blood counts should be performed until resolution of the event.
- If, after 42 days of interruption of rucaparib, the anemia has not improved to CTCAE Grade  $\leq 1$  then the patient should be referred to a hematologist and analysis of the bone marrow with cytogenetic studies are recommended according to standard hematologic practice.
- The bone marrow analysis should include a bone marrow aspirate (for cellular morphology, cytogenetic analysis, and flow cytometry) and a core biopsy (for bone marrow cellularity).

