## 8 STUDY CALENDAR

1 cycle = 28 days ( $\pm$  3 days)

Examination	Screening 	C1D1 	C(2+)D1 	PSA Progression Confirmation 	End of Treatment 	Follow-up 
Informed consent	X					
Treatment after PSA Progression ICF 				X		
Medical history	X					
Eligibility criteria 	X					
Vital signs	X	X	X	X	X	
Physical examination	X	X	X	X	X	
ECOG performance status	X	X	X	X	X	
Hematology 	X	X	X	X	X	
Chemistry 	X	X	X	X	X	
Lipid Panel 	X	X	X	X	X	
PSA 	X	X	X	X	X	X 
Urinalysis	X					
Coagulation Panel 	X					
Testosterone	X 					
ECG	X					
Adverse Event Assessment		X	X	X	X	
Concomitant Medication Review	X	X	X	X	X	
CT scans (c,a,p)	X			X 		
NM Bone Scans	X			X 		

Examination	Screening 	C1D1 	C(2+)D1 	PSA Progression Confirmation 	End of Treatment 	Follow-up 
Rucaparib administration 		X	X			
Blood for Correlative Studies 	X		X 	X 	X 	
Urine for Correlative Studies 	X		X 	X 	X 	
Archival Tissue for Correlative Studies 	X					
BRCAness Test 	X					
Optional biopsy 				X		
Survival Follow-up						X

1. All Pre-study/Screening procedures should be completed within 4 weeks of study enrollment. CT Scan and NM Bone scan do not need to be repeated if done within preceding 90 days of visit.
2. C1D1 procedures do not need to be repeated if screening procedures have been done within 7 days of start of treatment.
3. Cycles will continue at  $28 \pm 3$  days according to criteria in [Section 6.4](#).
4. Confirmation of BRCAness by previous result or prospective analysis of archival tissue or blood sample biopsy. If archival tissue is unavailable, a new biopsy will NOT be required.
5. Hematology includes CBC with differential and platelets.
6. Chemistry includes Albumin, Alkaline Phosphatase, Aspartate Aminotransferase, Alanine Aminotransferase, Total Bilirubin, Calcium, Carbon Dioxide, Creatinine, Chloride, Glucose, Potassium, Protein, Sodium, and Urea Nitrogen.
7. Lipid panel to consist of cholesterol, triglycerides, LDL cholesterol HDL Cholesterol, VLDL, and non-HDL Cholesterol.

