8. If treatment is discontinued prior to PSA progression, PSA testing will continue throughout follow-up until PSA progression or start of another treatment. Patients who have PSA progression prior to discontinuing treatment do not need to have PSA testing performed during follow-up.
9. Rucaparib will be administered as described in Section 6.
10. Blood collection for biomarkers will be collected at screening, C3D1, C7D1, and confirmed PSA disease progression ( $\pm 7$  days), if applicable, or at EOT visit (whichever occurs first).

11. For patients enrolled with an intact prostate, urine collection for biomarkers will be collected at screening, C3D1, C7D1, and confirmed PSA disease progression ( $\pm$  7 days), if applicable, or at EOT visit (whichever occurs first).
12. Archival tissue will be collected at screening (if available). Archival tissue should not be cut until instructed by the central lab.
13. Genomic or genetic testing for 'BRCAness' will be confirmed with either blood or tissue based testing.
14. An optional fresh tissue biopsy may be obtained at PSA Progression Confirmation Visit ( $\pm$  28 days) for subjects with radiographic disease progression.
15. CT scans of the chest/abdomen and pelvis and NM bone scans will be done at the time of PSA Progression Confirmation Visit ( $\pm$  28 days) as defined in section 10.1.
16. Follow-up should occur every 90 days ( $\pm$  14 days) for 2 years following End of Treatment as per standard of care (section 9).
17. Coagulation Panel includes PT/INR, PTT.
18. The end of treatment visit should occur within +/-3 days of the decision to discontinue treatment. If this visit overlaps with a regularly scheduled visit, only the procedures listed in the calendar for the EOT visit will be performed.
19. To be performed only if the subject has completed hormone therapy. Screening testosterone may be performed within 84 days of study enrollment.
20. Only patients who have suspected PSA progression during a regular study visit will have testing to confirm PSA progression at their next regularly scheduled visit. **Before continuation of treatment after confirmed PSA progression, the patient must agree to sign the Treatment After Progression Informed Consent Form.** Patients may complete the assessments required for PSA progression in conjunction with the next regularly scheduled cycle visit or at EOT.

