## **9.5 Follow-up Evaluations Q 90 days ( $\pm$ 14 days)**

Survival follow-up, including survival status and post-study treatments. Follow-up may be conducted via phone call or record review if laboratory assessments are not required.

- Laboratory assessments:
  - If treatment is discontinued prior to PSA progression, PSA testing will continue throughout follow-up until PSA progression or start of another treatment. Patients who have PSA progression prior to discontinuing treatment do not need to have PSA testing performed during follow-up.

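### Adverse events are due to day 30 and special-interest events beyond it, but no scheduled item collects them after the end-of-treatment visit

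*Combined protocol and SAP*

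**What the plan says.** The text sections set a broad duty. Section 15.4.1 fixes the window for adverse events (AEs): "Collection of adverse events will begin after the first dose of study treatment and end 30 days after the last dose of study treatment". Section 15.4.2 repeats it under serious adverse events (SAEs). Section 15.4.1 also says how AEs are found: "The occurrence of adverse events should be sought by non-directive questioning of the patient at each visit or phone contact during the study". Section 1.2.1, the endpoint for the first secondary objective, has AEs monitored in follow-up as well as during enrolment. Section 15.5, under the drug manufacturer notifications, extends reporting past day 30 to treatment-related SAEs and to every AESI, whether related or not. Section 15.4.3 instead ends AESI reporting at day 30. The two sections also differ on the time limit: 48 hours in 15.4.3 and 24 hours in 15.5.

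The operational sections are narrower. In the section 8 calendar, the row "Adverse Event Assessment" is marked at each cycle visit, the PSA progression confirmation visit and end of treatment (EOT). It is blank under Follow-up, where only PSA and survival are marked. Footnote 18 times the EOT visit: "The end of treatment visit should occur within +/-3 days of the decision to discontinue treatment". Footnote 16 sets what comes next: "Follow-up should occur every 90 days ( $\pm$ 14 days) for 2 years following End of Treatment". Section 9.5 describes the content of those contacts as "Survival follow-up, including survival status and post-study treatments", plus PSA for men who stopped before PSA progression. It allows a phone call or record review when no laboratory test is due.

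**The concern.** Staff work from the calendar and the visit lists. Followed as written, those ask about AEs for the last time at EOT, although the collection window stays open to day 30 after the last dose and one section keeps AESI and related-SAE reporting open after that. No contact is scheduled near day 30, and the next one has no AE or AESI item.

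Safety is the first secondary objective, and section 11.2 plans a descriptive tabulation. A table built on uneven ascertainment would count post-treatment events for men who happened to mention them or whose records happened to show them. A zero for late events would then carry little information, because it could mean that none occurred or that nobody asked. MDS/AML is the obvious example: section 3.1.6 discusses it under AESIs, and in the rucaparib programme a sizeable share of reports came late.

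**Working it through.** **Step 1. Duty against schedule**

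| Duty | Source | Scheduled item after EOT |
|---|---|---|
| AEs and SAEs to day 30 after last dose | 15.4.1, 15.4.2 | None in section 8 or 9.5 |
| AE monitoring in follow-up | 1.2.1 | None in section 8 or 9.5 |
| AE questioning at each visit or phone contact | 15.4.1 | Not listed in 9.5; cannot operate under record review |
| All AESIs and treatment-related SAEs after day 30 | 15.5 (15.4.3 stops AESIs at day 30) | None in section 8 or 9.5 |

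**Step 2. The gap in days**

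Inputs: EOT within 3 days of the decision to stop (footnote 18); follow-up every 90 ± 14 days from EOT (footnote 16); window to day 30 after the last dose (15.4.1).

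- First contact after EOT: 90 − 14 = 76 to 90 + 14 = 104 days.
- Let d be the days from last dose to EOT. The part of the 30-day window after the last scheduled AE assessment is 30 − d days for d between 0 and 30, and none beyond that.
- d = 0 leaves 30 days. d = 3 leaves 27. d = 14 (a two-week dose hold before the decision) leaves 16.
- With d = 0, the first contact comes 76 − 30 = 46 to 104 − 30 = 74 days after the window closes.

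The uncovered part therefore varies between men. The documents do not give the distribution of d.

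**Step 3. Reproduce the programme's MDS/AML rates**

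Inputs from section 3.1.6: 10 reports; 1077 patients exposed to oral rucaparib; 0.5% on treatment plus 28 days; "0.9% for all patients including during the long-term safety follow-up".

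- 10/1077 = 0.93%, which rounds to the stated 0.9%.
- For the 0.5%: 4/1077 = 0.37%, 5/1077 = 0.46%, 6/1077 = 0.56%. Only 5 rounds to 0.5%.
- Late reports: 10 − 5 = 5, about half.

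**Step 4. Apply the late rate to this trial**

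Input: 15 evaluable men (section 4.2). Assumption: the late programme rate carries over.

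- Expected late cases: 15 × 5/1077 = 0.07.
- Chance of at least one: 1 − (1 − 5/1077)^15 = 6.7%.
- With the rounded difference, 0.9% − 0.5% = 0.4%: expected 15 × 0.004 = 0.06; chance 1 − 0.996^15 = 5.8%.

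**Step 5. What a zero would show with complete ascertainment**

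With 0 of 15, the one-sided 95% upper limit is 1 − 0.05^(1/15) = 18.1%. That is already weak evidence; without systematic enquiry even that limit cannot be claimed.

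**The case against.** The strongest reply is that the plan already requires this. Section 1.2.1 includes follow-up, and section 15.4.1 requires questioning at every visit or phone contact during the study. Under section 6.4.3 a man who completes follow-up leaves the study only then, so follow-up calls count. A reader might infer from the calendar that nothing asks about AEs after EOT; these two sections rule that out. What stands is narrower. The instruction is absent from section 9.5 and the calendar, it has no effect when follow-up is by record review, and the same section closes AE collection at day 30, so staff at day 90 could reasonably regard AE questioning as finished.

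A reader might also infer that late events will be missed. The documents do not support that. Events can be volunteered, known AEs are followed to a new baseline (15.4.1), the safety committee reviews toxicities within 30 days of last treatment (15.3), treatment-related deaths after day 30 are reportable (15.4.2), and a record review or a list of later treatments may reveal a leukaemia. These routes depend on the event being known, volunteered, fatal or visible in the record. None looks systematically for a new, non-fatal event.

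Two further readings fail:

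- **A 13% chance of an MDS/AML case.** This comes from 10/1077, half of which arose on treatment or within 28 days. It does not measure the late gap.
- **The anaemia work-up.** Section 7.1.1 has a step beginning "If, after 42 days of interruption of rucaparib, the anemia has not improved to CTCAE Grade", which might seem to fall after all planned enquiry. But the 42 days run from dose interruption, and the same section gives weekly blood counts until resolution for persistent Grade 3 or worse or transfusion-dependent anaemia. Its heading also covers men who stop with ongoing anaemia.

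**Conclusion.** The point holds as a mismatch between what the protocol says it will collect and what its schedule collects. AE assessment is scheduled only up to EOT, nothing is scheduled near day 30, and the first later contact, 76 to 104 days after EOT, has no AE or AESI item and may not involve speaking to the patient. New non-fatal events after EOT may be missed or unevenly ascertained.

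For MDS/AML the size is small: 0.07 expected late cases, a 6.7% chance of at least one (5.8% from the rounded rates). It may be smaller still. The programme patients had multiple prior chemotherapy regimens, whereas section 5.2.8 excludes prior platinum, cyclophosphamide and mitoxantrone. Counting MDS/AML as an AESI rests on the heading of section 3.1.6, because the AESI list itself is in the Investigator's Brochure.

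The wider effect is on ordinary events in the 30-day window. It can concern any man whose EOT visit falls less than 30 days after his last dose. The documents give no rate from which to count the events lost. The primary endpoint is unaffected.

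**What to change.** In the Follow-up column of the section 8 calendar and in section 9.5, add:

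1. At the first 90-day contact: AEs and SAEs with onset up to day 30 after the last dose.
2. At every 90-day contact for the 2 years: AESIs, naming MDS/AML, and treatment-related SAEs.
3. When follow-up is by record review: abstraction of the same items, with the source noted, so that a zero means that someone looked.

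In section 15.4.1, state that the day-30 limit applies to general AEs and cross-refer to these items. Reconcile sections 15.4.3 and 15.5 on how long AESIs are reported and on the 48-hour or 24-hour limit.

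The cost is a few questions at contacts already planned and a line on the case report form; no new visit is needed. The weakness is recall: events in the 30-day window would be asked about at around day 90. A phone call at day 30 would remove that weakness but adds a contact.
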